2.6.1.1 RB, defined as positive if any tumor cells have RB nuclear staining

2.6.1.2 pRB, defined as positive if any tumor cells have phosphorylated-RB nuclear staining

2.6.1.3 p16, defined as positive if there is positive nuclear staining in 5% or more of tumor cells

2.6.1.4 Cyclin D1, defined as positive if any tumor cells have cyclin D1 nuclear staining

2.6.1.5 Ki67, defined as a percentage of positively stained cells (nuclear staining and mitotic figures) among the total number of malignant cells viewed in at least 3 randomly-selected high-power (x40 objective) fields

2.6.1.6 MCM7, defined as a percentage of positively stained cells (nuclei) among the total number of malignant cells viewed in at least 3 randomly-selected high-power (x40 objective) fields

2.6.1.7 pS6, defined using a histoscore of intensity and percent of tumor cells staining

2.6.2 Frequency of mutations (including, for example, *KRAS*, *CDKN2A*, *SMAD4*, and *TP53*) in the initial biopsy specimen from targeted NGS analyses from pre-treatment and on-treatment biopsy specimens

2.6.3 Frequency of mutations (including, for example, *KRAS*, *CDKN2A*, *SMAD4*, and *TP53*) from ctDNA as measured by quantitative PCR collected as detected in 5mL of serial blood samples collected every 8 weeks

2.7 Indication:

Patients with mPAC who have progressed on 5-FU- and GEM-based chemotherapy

3.0 SUBJECT POPULATION

3.1 Subject Population, Number of Subjects and Feasibility

(See Appendix C for Study Eligibility Checklist)

3.1.1 Subject Population

Patients with metastatic pancreatic adenocarcinoma whose disease has progressed on at least one 5-FU-based regimen and at least one GEM-based regimen for metastatic disease (progression during or within 3 months of the completion of adjuvant therapy is acceptable), and who have biopsiable disease, and who have an adequate performance status (PS), bone marrow, hepatic, and renal function

3.1.2 Number of Subjects

26 evaluable patients for the Phase II portion

3.1.3 Feasibility

Patients will be enrolled from the Lombardi Comprehensive Cancer Center (LCCC) at Georgetown University, and from partner institutions involved in this protocol. Only patients with mPAC will be eligible for enrollment. At our centers, over 300 new cases of pancreatic cancer are seen annually, at least one-half are metastatic, and around 25% of these patients would be eligible for further treatment after progression on 5-FU- and gemcitabine-based chemotherapy regimens. Therefore, around 18 patients would be eligible for enrollment in this trial each year. Based on this, we expect to accrue 1.5 patients per month, completing accrual in about 29 months.

3.2 Inclusion Criteria

1. Histologically confirmed mPAC (mixed histology is acceptable as long as the predominant histology is pancreatic adenocarcinoma)
2. Patient must consent to two mandatory biopsies and have tumor amenable to biopsy
 - Tumor biopsies are mandatory UNLESS the patient has been evaluated for a biopsy in consultation with radiology in good faith, and there is a determination that an attempt at a biopsy would cause undue risk to the patient.
3. Measurable disease by RECIST v1.1 criteria (tumor ≥ 1 cm in longest diameter on axial image on CT or MRI and/or lymph node(s) ≥ 1.5 cm in short axis on CT or MRI) on baseline imaging
4. Documented progression of disease on at least one 5-FU-based regimen and at least one GEM-based regimen for metastatic disease (progression during or within 3 months of the completion of adjuvant therapy is acceptable)
5. Eastern Cooperative Oncology Group (ECOG) performance status (PS) of 0-1 (see Table 2)
6. Age ≥ 18 years
7. Subjects with no brain metastases or a history of previously treated brain metastases who have been treated by surgery or stereotactic radiosurgery (SRS) at least 4 weeks prior to enrollment and have a baseline MRI that shows no evidence of active intracranial disease
8. Patients with available standard 12-lead ECG with the following parameters at screening (defined as the mean of the triplicate ECGs):
 - QTcF interval at screening <450 msec
 - Resting heart rate 50-90 bpm

9. Bone marrow function: absolute neutrophil count (ANC) $\geq 1,500/\text{mm}^3$; Platelets $\geq 100 \times 10^9/\text{L}$; hemoglobin $\geq 9.0 \text{ g/dL}$
 - Patients may have a transfusion of red blood cells to meet the hemoglobin requirement
10. Renal function: serum creatinine $\leq 1.5 \times$ upper normal limit of institution's normal range or creatinine clearance $\geq 50 \text{ mL/min/1.73 m}^2$ for subjects with creatinine levels above institutional normal
11. Hepatic function: AST and ALT $\leq 3.0 \times$ the upper normal limit of institution's normal range. Total bilirubin $\leq 1.5 \times$ the upper normal limit of institution's normal range. For subjects with liver metastases, AST and ALT $< 5 \times$ the upper normal limit of institution's normal range, and total bilirubin $> 1.5 - 3.0 \times$ the upper normal limit of institution's normal range are acceptable as long as there is no persistent nausea, vomiting, right upper quadrant pain or tenderness, fever, rash, or eosinophilia.
12. Partial Thromboplastin Time (PTT) must be $\leq 1.5 \times$ upper normal limit of institution's normal range and INR (International Normalized Ratio) ≤ 1.5 . Subjects on anticoagulant (such as warfarin) will be permitted to enroll as long as the INR is in the acceptable therapeutic range as determined by the investigator.
13. Potassium, total calcium (corrected for serum albumin), magnesium, sodium and phosphorus within normal limits for the institution or corrected to within normal limits with supplements before first dose of study medication
14. Patients must have fully recovered from all effects of surgery. Patients must have had at least two weeks after minor surgery and four weeks after major surgery before starting therapy. Minor procedures requiring "Twilight" sedation such as endoscopies or mediport placement may only require a 24-hour waiting period, but this must be discussed with an investigator.
15. Patients and their partners must avoid pregnancy during the trial, and for 21 days after stopping the study medications
 - Avoidance of pregnancy may include total abstinence when this is in line with the preferred and usual lifestyle of the patient. Periodic abstinence (e.g., calendar, ovulation, symptothermal, post-ovulation methods) and withdrawal are not acceptable methods of contraception
 - Eligible female patients may have undergone surgical bilateral oophorectomy with or without hysterectomy, total hysterectomy, or tubal ligation at least six weeks before taking study treatment. In case of oophorectomy alone, patients are eligible only when the reproductive status of the woman has been confirmed by follow up hormone level assessment
 - Eligible male patients and male partners of patients must also agree to avoid pregnancy during the trial, and for 21 days after stopping the study medications
 - Women of childbearing potential must have a negative serum pregnancy test within 14 days prior to initiation of treatment and/or postmenopausal women must be amenorrheic for at least 12 months to be considered of non-childbearing potential
16. Patient is capable of swallowing pills whole
17. Patient is capable of understanding and complying with parameters as outlined in the protocol and able to sign and date the informed consent, approved by the Institutional Review Board (IRB), prior to the initiation of any screening or study-specific procedures

Table 4. ECOG Performance Status

Grade	ECOG
0	Fully Active, able to carry on all pre-disease performance without restriction.
1	Restricted in physically strenuous activity but ambulatory and able to carry out work of a light or sedentary nature, e.g., light housework, office work.
2	Ambulatory and capable of all self-care but unable to carry out any work activities. Up and about more than 50% of waking hours.
3	Capable of only limited self care, confined to bed or chair more than 50% of waking hours.
4	Completely disabled. Cannot carry on any self-care. Totally confined to bed or chair.

3.3 Exclusion Criteria

1. Patients previously exposed to, intolerant of, or ineligible for CDK inhibitors, mTOR inhibitors, and/or their combination
2. Prior anti-tumor therapy within 3 weeks of Cycle 1 Day 1 (anti-tumor therapy defined as, but is not limited to, anti-cancer agents (cytotoxic chemotherapy, immunotherapy, and biologic therapy), radiotherapy, and investigational agents), the “wash-out period”
3. Patient has any other concurrent severe and/or uncontrolled medical condition that would, in the investigator’s judgment, cause unacceptable safety risks, contraindicate patient participation in the clinical study or compromise compliance with the protocol (e.g. chronic pancreatitis, chronic active hepatitis, active untreated or uncontrolled fungal, bacterial or viral infections, etc.).
4. Women who are pregnant or breastfeeding
5. Concurrent use of CYP3A4 inhibiting or activating medications
6. Concurrent use of an ACE inhibitor (increased risk of angioedema with ACE inhibitors administered in combination with everolimus, seen in approximately 6.8% of patients)
7. Psychiatric illness or social situation that would limit compliance with study requirements
8. Patient has a concurrent malignancy or malignancy within 3 years prior to starting study drug, with the exception of adequately treated, basal or squamous cell carcinoma, non-melanomatous skin cancer or curatively resected cervical cancer.
9. Patients with central nervous system (CNS) involvement unless they meet ALL of the following criteria:
 - At least 4 weeks from prior therapy completion (including radiation and/or surgery) to starting the study treatment
 - Clinically stable CNS tumor at the time of screening and not receiving steroids and/or enzyme-inducing anti-epileptic medications for brain metastases.
10. Patient has impairment of gastrointestinal (GI) function or GI disease that may significantly alter the absorption of the study drugs (e.g., ulcerative diseases, uncontrolled nausea, vomiting, diarrhea, malabsorption syndrome, or small bowel resection).
11. Patient has a known history of HIV infection or chronic, active Hepatitis B (testing not mandatory).

12. Patient has any other concurrent severe and/or uncontrolled medical condition that would, in the investigator's judgment, cause unacceptable safety risks, contraindicate patient participation in the clinical study or compromise compliance with the protocol (e.g. chronic pancreatitis, chronic active hepatitis, active untreated or uncontrolled fungal, bacterial or viral infections, etc.).
13. Clinically significant, uncontrolled heart disease and/or cardiac repolarization abnormalities, including any of the following:
- History of acute coronary syndromes (including myocardial infarction, unstable angina, coronary artery bypass grafting, coronary angioplasty, or stenting) or symptomatic pericarditis within 6 months prior to screening
 - History of documented congestive heart failure (New York Heart Association functional classification III-IV)
 - Documented cardiomyopathy
 - Left Ventricular Ejection Fraction (LVEF) <50% as determined by Multiple Gated acquisition (MUGA) scan or echocardiogram (ECHO) at screening
 - Clinically significant cardiac arrhythmias (e.g. ventricular tachycardia), complete left bundle branch block, high-grade AV block (e.g. bifascicular block, Mobitz type II and third-degree AV block)
 - Long QT syndrome or family history of idiopathic sudden death or congenital long QT syndrome, or any of the following:
 - Risk factors for Torsades de Pointe (TdP) including uncorrected hypokalemia or hypomagnesemia, history of cardiac failure, or history of clinically significant/symptomatic bradycardia.
 - Concomitant use of medication(s) with a known risk to prolong the QT interval and/or known to cause Torsades de Pointe that cannot be discontinued (within 5 half-lives or 7 days prior to starting study drug) or replaced by safe alternative medication
 - Inability to determine the QT interval on screening (QTcF, using Fridericia's correction)
 - Systolic blood pressure (SBP) >160 mmHg or <90 mmHg at screening
14. Patient is currently receiving any of the following medications and cannot be discontinued 7 days prior to starting study drug (see Table 4 for details):
- Known strong inducers or inhibitors of CYP3A4/5, including grapefruit, grapefruit hybrids, pummelos, star-fruit, and Seville oranges
 - That have a narrow therapeutic window and are predominantly metabolized through CYP3A4/5
 - Herbal preparations/medications, dietary supplements.
15. Patient is currently receiving or has received systemic corticosteroids ≤ 2 weeks prior to starting study drug, or who have not fully recovered from side effects of such treatment.
- Note: The following uses of corticosteroids are permitted: single doses, topical applications (e.g., for rash), inhaled sprays (e.g., for obstructive airways diseases), eye drops or local injections (e.g., intra-articular).

3.4 Prior and Concomitant Therapy

Any medication or vaccine (including over-the-counter or prescription medicines, vitamins and/or herbal supplements) that the subject is receiving at Screening up to the Final Visit must be recorded in source documents and the case report forms (CRFs). The reason for use, date(s) of administration (including start and end dates), and dosage information (including dose and frequency) must be recorded. Any change in concomitant therapy during the study period must be similarly recorded. Questions regarding prior or concomitant therapy should be directed to one of the investigators.

3.4.1 Prior Anti-cancer Therapy

For purposes of this protocol, anti-tumor treatment may be defined as, but is not limited to, anti-cancer agents (cytotoxic chemotherapy, immunotherapy, or biologic therapy), radiotherapy, and investigational agents. An investigational agent is any drug or therapy not currently approved for use in humans.

3.4.2 Prior Surgery

Patients must have fully recovered from all effects of surgery. Patients must have had at least two weeks after minor surgery and four weeks after major surgery before starting therapy. Minor procedures requiring “Twilight” sedation such as endoscopies or mediport placement may only require a 24 hour waiting period, but this must be discussed with an investigator.

3.4.3 Supportive Care

Subjects should receive best supportive care and treatment of symptoms during the study as appropriate, including transfusion of blood and blood products, oxygen therapy, nutritional support, intravenous fluids, and treatment with appropriate medications (antibiotics, antiemetics, antidiarrheals, and analgesics, etc.). Medications which are given for supportive care, such as appetite stimulation, may be given concurrently.

3.4.3.1 Bisphosphonates and denosumab

Bisphosphonates and denosumab are permitted for the treatment of osteoporosis and prevention of skeletal related events for patients with bone metastases. Chronic concomitant bisphosphonate/denosumab therapy for the prevention of bone metastasis is not permitted.

3.4.3.2 Hematopoietic growth factors

Hematopoietic growth factors may be used according to ASCO guidelines.

3.4.3.3 Palliative radiotherapy

Palliative radiation is permitted if done solely for bone pain relief. It should not be delivered to a target lesion and it should not encompass more than 25% of irradiated bone marrow. No dose modification of study treatment is needed during palliative radiotherapy.

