
	
Trial Auditing
 
The multi-institutional coordinator will arrange all primary source documents for the patients to be audited. This will include collecting copies of the primary source data for any patients treated at other sites.

Statistical Design, Feasibility, and Trial Duration
	
This is a multi-institutional single arm, open label Phase I/II study to evaluate the PFS_{8weeks} of the combination of LEE-011 plus everolimus, in patients with metastatic pancreatic cancer refractory to 5-fluorouracil (5-FU) and gemcitabine-based chemotherapy. Previous studies of third-line therapy in mPAC are limited but reveal stable disease in 25-31% of patients with no partial or complete responses (31% of patients in the GVAX/CRS-207 combination vaccine study had stable disease but only 52% of these patients were treated in the third-line setting)^(5, 6). It is hoped that the combination of LEE-011 plus everolimus can increase the PFS_{8weeks} to at least 50%, though early stopping rules are in place for lack of efficacy.
 
All patients meeting the eligibility criteria and who have signed a consent form, have begun treatment, are not lost to follow-up, and are not taken off study for reasons other than progression or death before 8 weeks will be considered evaluable for the assessment of the DCR.
 
Between 12 and 24 patients will be enrolled in the Phase I portion of the study, depending on whether DLTs occur and dose de-escalation is required. The 6 patients treated at the RP2D will be included in the Phase II portion of the study. We anticipate the combination will be well tolerated such that all of the patients in the Phase I portion are likely to be evaluable for the Phase II efficacy analysis.
 
26 evaluable patients will be enrolled in the Phase II portion of the study (though the potential drop-out rate is 10%), which will provide a 90% power to detect an improvement in the DCR from 25% (based on historical control) to 50%, assuming a 1-sided significance level of 0.1 and an accrual rate of 2 patients per month. A Simon's optimal two-stage design will be used to test the null hypothesis that the DCR $P \leq 0.25$ versus the alternative that $P > 0.5$. For the first stage, 11 patients will be entered to the study. The trial will be terminated if 2 or fewer patients achieve a PR, CR, or SD at 8 weeks. If at least 3 patients in the first stage achieve a PR, CR, or SD at 8 weeks, the trial goes on to the second stage. A total of 26 patients will be enrolled. If the total number of patients who achieve a PR, CR, or SD at 8 weeks is less than or equal to 9, the combination therapy will be rejected. If however, 10 or more patients achieve a PR, CR, or SD at 8 weeks the combination therapy will be considered for further analysis.
 
With 26 evaluable patients in the Phase II portion, combined with a minimum of 12 to a maximum of 18 patients enrolled strictly in the Phase I portion of the trial, there will be up to 44 patients enrolled. At an expected accrual rate of 3 patients per month, the expected accrual duration will be approximately 15 months.
 
Descriptive statistics will be used to summarize patients' demographics, toxicity, and quality of life. The PFS_{8weeks} will be estimated from the observed data with 95% exact binomial confidence interval. The nonparametric Kaplan-Meier method will be used to estimate the survival function and calculate the PFS and OS. The ORR will be estimated from the observed data with 95% exact binomial confidence intervals.

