Herbal preparations/medications	Herbal preparations/medications known as strong inducers or inhibitors of CYP3A4/5 or those with a known risk of QT prolongation are prohibited throughout the study. These herbal medications include, but are not limited to: St. John's wort, Kava, ephedra (ma huang), ginkgo biloba, dehydroepiandrosterone (DHEA), yohimbe, saw palmetto, and ginseng. Patients should stop using these herbal medications 7 days prior to first dose of study drug.
Other investigational and antineoplastic therapies	Other investigational therapies must not be used while the patient is on the study. Anticancer therapy (chemotherapy, all SERMS (including raloxifene), biologic or radiation therapy, and surgery) other than the study treatments must not be given to patients while the patient is on the study medication. If such agents are required for a patient then the patient must be discontinued study drug.

¹ NTI = narrow therapeutic index drugs whose exposure-response indicates that increases in their exposure levels by the concomitant use of potent inhibitors may lead to serious safety concerns (e.g., Torsades de Pointes) or drugs which have <2-fold difference in the minimum toxic concentrations and minimum effective concentrations in the blood.

² Herbal product

³ P-gp inducer

⁴ The list provided is as of January 2018. Check <https://www.crediblemeds.org/healthcare-providers/drug-list> for the most updated list.

As far as possible, avoid co-administration of QT prolonging drugs or any other drugs with the potential to increase the risk of drug-related QT prolongation (e.g., via a potential DDI that increases the exposure of ribociclib or the exposure of the QT prolonging drug). A definitive list of drugs with a known risk, possible risk, or conditional risk of QT prolongation and/or Torsades de Pointes (TdP) is available online at qtdrugs.org.

Source: Novartis PK Sciences Memorandum: Drug-Drug Interactions (DDI) and Co-medication Considerations for Novartis Clinical Trials (January 2018), which is compiled from Indiana University "Clinically Relevant" Flockhart Table™, University of Washington Drug Interaction Database, and FDA Drug Development and Drug Interactions: Table of Substrates, Inhibitors and Inducers.

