4.4.9 Removal of Subjects from Therapy or Assessment

4.4.9.1 Reasons for Removal of Subjects from Therapy or Assessment

Each subject has the right to withdraw from study treatment at any time. In addition, the investigator may discontinue a subject from the study treatment at any time for any reason if the investigator considers it necessary, including the occurrence of an adverse event or noncompliance with the protocol. Each subject will be withdrawn from the study if any of the following occur:

- 1) The subject experiences either clinical or radiographic progressive disease.
- 2) The subject requires radiotherapy or alternate antineoplastic agents during the study period.
- 3) The investigator believes it is in the best interest of the subject.
- 4) Clinically significant deterioration of the subject's medical status as determined by the investigator.
- 5) Subject becomes pregnant or begins breastfeeding during the treatment portion of the study.
- 6) The subject or subject's legally acceptable representative decides to withdraw consent for any reason.
- 7) Any other medical reason that the study investigator deems appropriate.

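### The protocol both permits bone-pain radiation on unchanged study drug and requires withdrawal of any patient who needs radiotherapy, so such a patient's week-8 status is not fixed

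*Combined protocol and SAP*

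**What the plan says.** **Permission.** Section 3.4.3.3, under Supportive Care: "Palliative radiation is permitted if done solely for bone pain relief". The radiation may not go to a target lesion and is limited in marrow extent. Study drug continues: "No dose modification of study treatment is needed during palliative radiotherapy".

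**Withdrawal.** Section 4.4.9.1 opens: "Each subject will be withdrawn from the study if any of the following occur". Item 1 is progressive disease, clinical or radiographic. Item 2 is: "The subject requires radiotherapy or alternate antineoplastic agents during the study period". Item 2 has no exception for bone pain and no reference to 3.4.3.3.

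**Progression.** Section 7.4 item 2 defines clinical progression by investigator judgement. Its item 2b gives a need for palliative radiation as one possible form, again without a bone-pain exception.

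**Prohibited therapy.** The last row of Table 6 (Section 3.4.6), on investigational and antineoplastic therapies, says that anticancer therapy including "biologic or radiation therapy, and surgery) other than the study treatments must not be given to patients" on study medication, and adds: "If such agents are required for a patient then the patient must be discontinued study drug".

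**Primary endpoint and evaluable set.** Sections 2.4 and 9.4.1 define week-8 success by RECIST imaging read by radiologists. The synopsis (Statistical Design, Feasibility, and Trial Duration) says that treated patients who, among other conditions, "are not taken off study for reasons other than progression or death before 8 weeks will be considered evaluable". Section 9.5.1 sets the decision: continue with 3 or more of 11, declare success with 10 or more of 26.

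**The concern.** The same patient meets one rule that keeps them on unchanged study drug and another that takes them off study. Item 2 of 4.4.9.1 is separate from progression in item 1. A withdrawal under item 2 is therefore, on its face, for a reason other than progression or death, and the synopsis sentence then removes the patient from the evaluable set.

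The primary result is a count against fixed cut-offs in an open-label, multi-institutional trial. Whether a stable patient is in that count should be settled before the scan is read. The same conflict decides whether a patient who needs pain relief keeps study drug.

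**Working it through.** **1. Follow one patient through the text.** Take a patient with RECIST-stable disease who is irradiated at week 5 for pain from a non-target bone lesion.

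| Sections followed | On study? | Week-8 status |
|---|---|---|
| 3.4.3.3, then 9.4.1 | Kept, drug unchanged | Scored on the scheduled scan; success if still stable |
| 4.4.9.1 item 2, then the synopsis evaluability sentence | Withdrawn | Non-evaluable |
| 7.4 item 2b, then 4.4.9.1 item 1 | Withdrawn as clinical progression | Evaluable under the synopsis sentence, but 2.4 and 9.4.1 score on imaging, so the score is not stated |

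No section says which route prevails.

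**2. Reproduce the design.** Inputs from 9.3 and 9.5.1: null rate 0.25, alternative 0.50, one-sided alpha 0.10, power 90%, stop at 2 or fewer of 11, success at 10 or more of 26.

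P(go) = sum over x = 3 to 11 of P(Bin(11, p) = x) × P(Bin(15, p) ≥ 10 − x)

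- p = 0.25: 0.0857, within the 0.10 limit
- p = 0.35: 0.4088
- p = 0.50: 0.9005, against 90% stated

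The stated design reproduces. Scoring irradiated patients on their scheduled scans leaves these figures as they are.

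**3. Illustrate the second route.** The documents give no irradiation rate. Assume that a share q of would-be successes is irradiated before week 8, dropped and replaced. Among the remaining patients the success rate is p(1 − q)/(1 − pq). For p = 0.50 and q = 0.05 this is 0.475/0.975 = 0.4872.

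| Assumed q | Rate at p = 0.50 | P(go) at 0.50 | Fall from 0.9005 | Fall at p = 0.35 | Fall at p = 0.25 |
|---|---|---|---|---|---|
| 0.02 | 0.4949 | 0.8917 | 0.0089 | 0.0189 | 0.0071 |
| 0.05 | 0.4872 | 0.8769 | 0.0237 | 0.0474 | 0.0170 |
| 0.10 | 0.4737 | 0.8479 | 0.0527 | 0.0950 | 0.0319 |

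The expected number of would-be successes affected per 26 patients at p = 0.50 is 26 × 0.50 × q = 0.26, 0.65 or 1.30.

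**4. Limits of that illustration.**

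- The values of q are assumed.
- It takes only would-be successes as irradiated. If irradiation is unrelated to week-8 outcome, the rate among evaluable patients does not change.
- It replaces treated patients. Only the synopsis allows that, for up to 3 patients. Sections 4.1.2 and 9.2 limit replacement to patients who were screened but did not start treatment in time.
- Without replacement, losing one stage-2 patient regardless of outcome, with the cut-off still at 10, gives P(go) of 0.0683 at 0.25 and 0.8734 at 0.50. That count of one is also assumed.

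**The case against.** The strongest reply is that ordinary reading resolves the conflict. Section 3.4.3.3 is narrow and sits among other supportive-care carve-outs. If 4.4.9.1 item 2 overrode it, its sentence on study drug could never apply. This stands as the best account of intent. It does not remove the defect: item 2 is mandatory and unqualified, and the corticosteroid rule in 3.4.3.4 shows that the protocol writes out its exceptions when it wants them.

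Two other sections seem to strengthen the conflict but add little. Section 3.4.1 says that "anti-tumor treatment may be defined as, but is not limited to, anti-cancer agents (cytotoxic chemotherapy, immunotherapy, or biologic therapy), radiotherapy, and investigational agents", but it sits under prior therapy. The Table 6 row is about anticancer therapy, so radiation for pain can fairly be read as outside it. The case rests on 4.4.9.1 and 7.4.

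It is also fair to say that the exclusion of early withdrawals is a general evaluability question. The sentence stands only in the synopsis and is worded for disease control rate, while 9.4.1 says that each patient is categorised. Bone-pain radiation is one uncommon trigger of that question.

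A reader might infer stronger conclusions, which the documents do not support:

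- **The trial is underpowered.** The power losses shown rest on assumed shares and on a replacement rule that 9.2 does not grant.
- **These patients would be scored as failures.** At p = 0.50 that would give 0.8824, 0.8509 or 0.7862 for the same shares, but 2.4 and 9.4.1 score on imaging, and 7.4 item 2b is discretionary.
- **Keeping these patients inflates the false-positive rate.** That requires counting them as successes whatever the scan shows. Scored on the scan, the rate stays at 0.0857.
- **Sites will count identical patients differently.** They could, but data go to one database and response is reviewed monthly across sites, so this is a risk and not a prediction.

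**Conclusion.** The text is wrong as written: 3.4.3.3 and 4.4.9.1 item 2 give opposite instructions for the same patient, and 7.4 item 2b opens a second route to withdrawal. This is a conflict between stated rules and not merely missing detail. Severity is minor. The likely intent is clear, few patients are likely to be affected, and the effect on the primary result is probably small. Its size cannot be derived, because the irradiation rate, its relation to week-8 outcome and the governing replacement rule are all either absent or unsettled. The sample size of 26, alpha, power and both cut-offs stand.

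**What to change.** 1. In 4.4.9.1 item 2, add: *except palliative radiation for bone pain permitted under 3.4.3.3*.
2. Add the same exception to 7.4 item 2b. This is a necessary part of the repair; otherwise the patient can still be withdrawn through item 1 as clinical progression.
3. For clarity, add it to the antineoplastic row of Table 6.
4. In 9.4.1, state that these patients stay evaluable and are scored on the scheduled week-8 RECIST scan.

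If the clinical team does not want the exception, delete 3.4.3.3 instead and state in 9.4.1 how a patient withdrawn for radiotherapy is counted.

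The cost is one phrase in three places and one sentence in 9.4.1. No patients, procedures or analyses are added.
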